3.2 STUDY ENDPOINTS

PRIMARY ENDPOINT

Objective	Endpoint	Start	End
Observed rate of brain metastases following TTFields therapy at 6 months	Incidence of SCLC brain metastases at 6 mo	Start of TTFields [baseline]	6 mo

SECONDARY ENDPOINTS

Objective	Endpoint	Start	End

Observed rate of brain metastases following TTFields therapy at 12 months	Incidence of any SCLC brain metastases at 12 mo	Start of TTFields [baseline]	12 mo
Overall survival of participants with SCLC after using TTFields therapy.	Overall survival	Start of TTFields [baseline]	Death or last follow-up at 60 months.
TTFields therapy related side effects.	1. Incidence of TTFields related AEs 2. Incidence of cognitive AEs using Mini Mental State Exam (MMSE)	Start of TTFields [baseline]	12 mo 6, 12 mo 12 mo
Quality of life among participants using TTFields therapy.	EORTC QLQ-C30 questionnaire at 6 and 12 mo	Start of TTFields [baseline]	6, 12 mo
Observed rate of SCLC brain metastases at 6 month from the beginning of the 4 th cycle of chemotherapy to development of brain metastases	Incidence of SCLC brain metastases at 6 month from the beginning of the 4 th cycle of chemotherapy to development of brain metastases	Start of the 4 th cycle of chemotherapy [baseline]	6 mo

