4. STUDY ENROLLMENT AND WITHDRAWAL

4.1 PARTICIPANT INCLUSION CRITERIA

To be eligible to participate in this study, an individual must meet all of the following criteria:

1. Ability to understand and the willingness to sign a written informed consent document.
2. Age ≥ 22 years at time of informed consent. Both men and women and members of all races and ethnic groups will be included.
3. Pathologically confirmed LS-SCLC or ES-SCLC.
 - a. LSCLC – Stage I-III (T_{any}, N_{any}, M0) that can be safely treated with radiation doses. Excludes T3-4 due to multiple nodules that are too extensive or have tumor/nodal volume that is too large to be encompassed in a tolerable radiation plan.¹⁹
 - b. ESCLC – Stage IV (T_{any}, N_{any}, M1), or T3-4 due to multiple nodules that are too extensive or have tumor/nodal volume that is too large to be encompassed in a tolerable radiation plan.¹⁹
4. Must be no more than 6 weeks from having received last dose of chemo- and/or radiotherapy for primary tumor to anticipated start of TTField therapy.
5. Partial response to standard of care (chemo- and/or radiotherapy) as judged by treating physicians with no evidence of recurrence as observed by thoracoabdominal CT within 12 weeks of enrollment.
6. No brain metastases as observed by gd-MRI within 12 weeks of enrollment.
7. No previous or currently active second malignancy, with exception of non-metastatic prostate cancer, treated Stage I breast cancer, skin malignancies.
8. Life expectancy of at ≥ 3 months.
9. ECOG performance status ≤ 2 (Karnofsky ≥ 60 ; Refer to **Appendix A**).
10. Participants must be willing and able to fully comply with the minimum required 18 hours/day of TTField therapy.
11. Women of child-bearing potential must agree to use adequate contraception (hormonal or barrier method of birth control; abstinence) prior to study entry and for the duration of study participation.

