7.4 ASSESSMENTS DURING TREATMENT

Refer to the schedule of events (Section 7.8) for timing and details of specific procedures to be conducted. Except for head MRI scans that is scheduled every three months for the 1st year while participants are on-treatment, all other imaging will be in accordance with standard-of-care guidelines. Clinical evaluations are scheduled to occur every two months for ES-SCLC patients, and every three months for LS-SCLC patients while participants are on-treatment. Follow-up phone calls will occur every other month for months patients are not seen for clinical evaluation at the clinic. Follow-up and clinical evaluations will resume to standard-of-care after completion of the treatment period. Imaging can be done within \pm 1 week. All other studies can be obtained \pm 3 days of the stated time point.

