10.1 ANALYSIS POPULATIONS

This is a phase II multi-center single-arm pilot study to evaluate the incidence of metastatic brain lesions in participants with SCLC that receive TTField therapy. All participants that initiated TTField therapy will be considered evaluable for efficacy analysis. All participants who initiated TTFields therapy (regardless of duration) will be considered evaluable for safety. The anticipated enrollment is 106 participants, of which 45 participants will have ESCLC and 61 participants will have LSCLC.

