The distribution of overall survival will be graphically described using Kaplan-Meier plot, for all subjects together, and for each disease group (extensive stage and limited stage). If estimable, the median survival time will be reported with 95% confidence interval. The analysis is just for description. No hypothesis testing is planned for this endpoint. However, we will fit two cox

proportional hazard regression model to identify risk factors that may impact the OS. Covariates evaluated in the univariable analysis in Section 10.2.1 will also be evaluated in the cox proportional hazard regression model. OS at 6, 12, 24, 36 and 60 months after completion of TTField therapy will be reported.

We will estimate TTField therapy-related toxicity and along with an exact confidence interval using the safety set. A summary table of observed AEs will also be reported by disease group (extensive stage and limited stage).

The Quality of life scores will be recorded over time (See Section 7.8 for details) using the EORTC QLQ-C30 questionnaire. Summary of QoLs and its change over time will be presented graphically using box plot and spaghetti plot, in addition to a summary table of QoL over time. No hypothesis testing is planned for QoL.

Incidence of cognitive AEs will be assessed by measuring changes in MMSE scores over time. Descriptive statistical analysis will be conducted on the endpoint. (See Section 7.8 for details on time points for measurement)

To evaluate how the time of last cycle of chemotherapy or chemoradiation therapy impact our observed incidence of SCLC brain metastases, we will also conduct a parallel analysis using SCLC brain metastases rate at 6-month from the beginning of the 4th cycle of chemotherapy to development of brain metastases as a secondary endpoint. We will use exactly the same approach as described in Section 10.2.1.

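### The secondary endpoint timed from the 4th chemotherapy cycle starts before participants can enter the trial and has no scan rule, so its test against 40% and 30% is not valid

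*Combined protocol and SAP*

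**What the plan says.** - **Time zero.** The secondary endpoint table in Section 3.2 starts this endpoint at the 4th cycle of chemotherapy and ends it 6 months later. The primary endpoint in the same section starts at TTFields start, which Section 4.5 calls Day 1.
- **Purpose.** Section 10.2 gives the aim as "To evaluate how the time of last cycle of chemotherapy or chemoradiation therapy impact our observed incidence of SCLC brain metastases", and to that end states "we will also conduct a parallel analysis using SCLC brain metastases rate at 6-month from the beginning of the 4th cycle of chemotherapy".
- **Analysis.** For this endpoint Section 10.2 says "We will use exactly the same approach as described in Section 10.2.1". That approach is a one-sample test of the proportion against 40% (ES) and 30% (LS), plus logistic models.
- **Entry.** Section 4.1 item 4 reads "Must be no more than 6 weeks from having received last dose of chemo- and/or radiotherapy for primary tumor", counted to the anticipated start of TTFields. Item 6 requires "No brain metastases as observed by gd-MRI within 12 weeks of enrollment". No number of chemotherapy cycles is required.
- **Analysis set.** Section 10.1: "All participants that initiated TTField therapy will be considered evaluable for efficacy analysis".
- **Scans.** Section 7.4 refers to "head MRI scans that is scheduled every three months for the 1st year while participants are on-treatment" and allows 1 week either side. The grid in Section 7.8 places them at weeks 12, 24 and 36 of treatment.
- **Missing time points.** Section 10.4 allows other time points to be considered where one has no data, and rules out imputation.

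**The concern.** A patient whose brain metastasis is found after cycle 4 but before TTFields start fails eligibility, never starts the device and is not in the analysis set. Such an event can never be counted, although the interval in which it occurs is part of the 6 months being measured. This is immortal time with respect to detected events, and nothing in Section 10.2 adjusts for it.

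The scan calendar adds a second problem. Scans follow Day 1, the landmark follows cycle 4, and the plan does not say which scan decides 6-month status.

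The analysis is meant to show how chemotherapy timing affects the result. As planned, it mixes timing with selection at entry and with scan timing, and attaches a p-value that could be read as support for the device. Anyone who had fewer than four cycles has no time zero at all.

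**Working it through.** **1. The plan's own figure.** Section 10.3 gives 45 ES (40% to 20%) and 61 LS (30% to 15%) for 80% power with a two-sided exact 5% test. With at most 2.5% per tail:
- ES, n=45: a reduction is declared at 11 or fewer events. Lower-tail error is 2.2% and power is 82.6%.
- LS, n=61: a reduction is declared at 11 or fewer events. Lower-tail error is 2.5% and power is 80.4%.

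Both sample sizes reproduce. The same cut-offs carry over to this endpoint.

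**2. Assumptions.** Let L be the weeks from cycle 4 start to Day 1. The documents do not give L, so it is shown as a range. Six months is taken as 26 weeks. The hazard is constant and set so that 26-week incidence equals the null p0. The device has no effect, and deaths are ignored. Cumulative incidence over w weeks is then 1 − (1 − p0)^(w/26).

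**3. Where the landmark falls.** It is on-device week 26 − L. For L = 4 to 12 that is weeks 22 to 14, between the week-12 and week-24 MRIs. For L of about 1 to 3 it is weeks 25 to 23, within the 1-week window of the week-24 MRI.

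**4. Lead-in contributes no events; detection is continuous up to the landmark.** Here w = 26 − L. Example, ES with L = 6: 1 − 0.6^(20/26) = 32.5%. The false-positive rate is the binomial probability of 11 or fewer events at the resulting incidence.

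| L (weeks) | ES incidence | ES false positive | LS incidence | LS false positive |
|---|---|---|---|---|
| 3 | 36.4% | 6% | 27.1% | 7% |
| 6 | 32.5% | 16% | 24.0% | 17% |
| 12 | 24.0% | 60% | 17.5% | 62% |

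**5. Other scan rules the text permits, L = 4 to 12.**
- Only the week-12 MRI counts, with status clear at Day 1 (w = 12): ES 21.0%, LS 15.2%; false positives 78% and 79%.
- Only the week-12 MRI counts, but the entry MRI was taken at or before cycle 4, so lead-in lesions surface at week 12 (w = 12 + L): ES 27.0% to 37.6%, LS 19.7% to 28.1%.
- The week-24 MRI stands in under Section 10.4 (w = 24): ES 37.6%, LS 28.1%; false positives 4.5% and 5.0%.
- The week-24 MRI with an early entry MRI (w = 24 + L): ES 42.3% to 50.7%, LS 31.9% to 39.0%, above the null.

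So with no treatment effect at all, the ES proportion could be about 21% or about 51%, depending on the gap, the date of the entry scan and a scan rule that is not stated.

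**The case against.** A reader might infer that this endpoint is always biased downward, that the lead-in is free of events by design, or that no MRI ever meets the landmark. The documents support none of these as absolutes. The entry MRI may be up to 12 weeks old and so may predate cycle 4; the lead-in is then free of detected events but not of lesions, which can surface later and be counted. With a gap of about 1 to 3 weeks the week-24 MRI does meet the landmark. Section 10.4 may bring in the week-24 scan, and Section 7.7 allows unscheduled assessments. These objections stand, and they remove any fixed direction of bias. They do not rescue the test, because they show that its null behaviour depends on choices the plan leaves open.

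The 60-62% figures are also an extreme: they need every participant to have a 12-week gap. Spreading the gap evenly over 3 to 12 weeks (mean 7.5, so about 18.5 weeks counted) gives roughly 24% (ES) and 26% (LS), still about ten times nominal.

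Nor would the problem persist under every benchmark. The 40% and 30% are given no time origin. A benchmark drawn from patients already free of detected metastases at the same point would remove the lead-in inflation, but the plan does not say that its rates are of that kind, and it uses the same rates for two different clocks.

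Finally, Section 10.4 permits endpoint-specific exclusions with reasons, which partly covers participants with fewer than four cycles. And this is one secondary, parallel analysis in a pilot study, which limits what is at stake.

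**Conclusion.** The point holds in this form. The endpoint's clock starts before entry, metastases detected in the lead-in are excluded by eligibility and by the analysis set, the scan that defines 6-month status is not specified, and the proportion is still tested against unadjusted 40% and 30%. If no other time point is substituted, a device with no effect would appear to reduce incidence, with false-positive rates from about 6-7% (3-week gap) to 60-62% (12-week gap), against 2.2-2.5%. If the week-24 MRI is used instead, the bias nearly disappears or turns upward. In none of these cases does the test keep its nominal error in a way the plan secures. Where the calculated rate equals the null, as with a 2-week gap, an early entry MRI and the week-24 scan (24 + 2 = 26), it does so by coincidence.

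The sizes rest on the assumed gap, a constant hazard, no competing deaths, and the historical rates applying from cycle 4. The structural finding needs none of these. The primary endpoint, timed from TTFields start, does not have this lead-in problem.

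**What to change.** In Section 10.2, for this endpoint only, remove the one-sample test and the sentence that carries over the primary approach.

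To answer the stated question about chemotherapy timing, keep Day 1 as time zero and add weeks from cycle 4 start to Day 1 as a baseline covariate in the logistic models already planned.

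If a rate from cycle 4 is still wanted, report it descriptively:
- restrict it to participants who received a 4th cycle;
- count participants only from TTFields start (delayed entry), and describe the rate as conditional on no detected brain metastasis at entry;
- state in advance one rule for which scan defines 6-month status.

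Keeping a test with a null restated for event-free entry is less attractive. For a halving of incidence at gaps of 2, 6 and 12 weeks, power at the planned sizes would be 79%, 70% and 36% (ES) and 65%, 55% and 38% (LS).

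The cost is wording and one lost secondary p-value. No visit or scan is added, and the cycle-4 date is already needed for the endpoint.

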10.3 SAMPLE SIZE, POWER, ACCRUAL RATE AND STUDY DURATION

SAMPLE SIZE AND POWER

A total of 106 participants with SCLC will be accrued into this study of which 45 and 61 participants will be characterized as having either ESCLC or LSCLC disease, respectively. For ESCLC, we need 45 subjects for 80% power to detect a 50% reduction at a 5% significance level using a two-sided exact test for one proportion, assuming the incidence rate is 40% for subjects not receiving Optune®. PASS 15 “Test for one proportion” procedure was used for sample size computation. We will use two-sided exact test for one proportion to test the incidence rate against the null hypothesis of 40%. $P < 0.05$ will be considered statistically significant.

For participants with LSCLC, we need 61 subjects for 80% power to detect a 50% reduction at a 5% significance level, using a two-sided exact test for one proportion, assuming the incidence rate is 30% for subjects not receiving Optune®. PASS 15 “Test for one proportion” procedure was used for sample size computation. We will use two-sided exact test for one proportion to test the incidence rate against the null hypothesis of 30%. $P < 0.05$ will be considered statistically significant.

10.4 HANDLING OF MISSING DATA

Every attempt will be made to obtain data at the defined time points as described in the primary and secondary endpoints. For time points that have no data, we will evaluate whether or not the other time points can be used to fulfill the primary and secondary data. If the data are not sufficient to analyze specific endpoints, the participant's data may be excluded entirely or

partially, depending on the specific endpoints in question and in consultation with the biostatistician. No missing data will be imputed. Whenever possible, all available data will be included in the analysis. A sample size for each analysis will be clearly stated along with the reason for exclusion, if any participant is excluded from the analysis due to missing data.

11. CLINICAL MONITORING

11.1 OHSU KNIGHT CANCER INSTITUTE DATA & SAFETY MONITORING PLAN

This study is under the oversight of the Knight Cancer Institute's DSMC as described in the Knight institutional DSMP. The Knight DSMP outlines the elements required to ensure the safety of clinical trial participants, the accuracy and integrity of the data and the appropriate modification of cancer-related clinical trials for which significant benefits or risks have been discovered or when the clinical trial cannot be successfully concluded. The Knight DSMP also describes the methods and procedures for ensuring adequate oversight of cancer-related research at OHSU.

As described in the Knight DSMP, regardless of a trial's risk level and any specific Knight oversight in place, the Investigator is singularly responsible for overseeing every aspect of the design, conduct, and final analysis of his/her investigation.

The Knight DSMC will review and monitor study progress, toxicity, safety and other data from this study. Information that raises any questions about participant safety or protocol performance will be addressed by the Investigator, statistician and study team. Should any major concerns arise, the Knight DSMC may recommend corrective action and determine whether or not to suspend the study.

The Knight DSMC will review each protocol every 6 months, but may occur more often, if required, to review toxicity and accrual data (please refer to Knight DSMP for additional details on audit frequency). The Knight DSMC will review accrual, toxicity, response and reporting information. Information to be provided to the DSMC may include: participant accrual; treatment regimen information; AEs and SAEs reported by category; summary of any deaths on study; audit results; and a summary provided by the study team. Other information (e.g. scans, laboratory values) will be provided upon request.

11.2 CLINICAL DATA & SAFETY MONITORING

The OHSU Investigator is ultimately, singularly responsible for overseeing every aspect of the investigation, including design, governing conduct at all participating sites, and final analysis of study data.

In the absence of a formal monitoring plan, the Investigator may work with his/her study team to conduct and document internal monitoring of the study to verify protection of human participants, quality of data, and/or ongoing compliance with the protocol and applicable regulatory requirements.

If at any time Investigator noncompliance is discovered at OHSU, the Investigator shall promptly either secure compliance or end the study with participating site.

Independent audits will be conducted by the Knight DSMC to verify that the rights and well-being of human participants are protected, that the reported trial data are accurate, that the conduct of the trial is in compliance with the protocol and applicable regulatory requirements, and that evidence of ongoing investigator oversight is present.

11.3 QUALITY ASSURANCE & QUALITY CONTROL

The investigational site will provide direct access to all trial related source data/documents, and reports for the purpose of monitoring by the monitor and/or sponsor, and auditing by the Knight DSMC and/or regulatory authorities.

Quality assurance (QA) auditing activities will occur as detailed in the Knight DSMP. All discrepancies, queries, deviations, observations, and findings will be compiled into a final audit report along with a Corrective and Preventative Action Plan.

The Sponsor-investigator, or study monitor, will verify that the clinical trial is conducted and data are generated, documented (recorded), and reported in compliance with the protocol, GCP, and the applicable regulatory requirements (e.g., Good Laboratory Practices (GLP), Good Manufacturing Practices (GMP)).

12. DATA HANDLING AND MANAGEMENT RESPONSIBILITIES

12.1 SOURCE DATA/DOCUMENTS

The Investigator is responsible for ensuring the accuracy, completeness, legibility, and timeliness of the data reported. All source documents should be completed in a neat, legible manner to ensure accurate interpretation of data. The Investigator will maintain adequate case histories of study participants, including accurate CRFs and source documentation.

12.2 PARTICIPANT & DATA CONFIDENTIALITY

The information obtained during the conduct of this clinical study is confidential, and unless otherwise noted, disclosure to third parties is prohibited. Information contained within this study will be maintained in accordance with applicable laws protecting participant privacy, including the provisions of the Health Insurance Portability and Accountability Act (HIPAA).

Participant confidentiality is strictly held in trust by the participating Investigator(s) and study team. This confidentiality is extended to cover testing of biological samples and genetic tests in addition to the clinical information relating to participants. Therefore, the study protocol, documentation, data, and all other information generated will be held in strict confidence. No information concerning the study or the data will be released to any unauthorized third party without prior written approval of the sponsor.

The study monitor, other authorized representatives of the sponsor, representatives of the IRB or manufacturer supplying study product may inspect all documents and records required to be maintained by the Investigator, including but not limited to, medical records (office, clinic, or hospital) and pharmacy records for the participants in this study. The clinical study site will permit access to such records.

Upon enrollment, participants will be assigned a code that will be used instead of their name, medical record number or other personally identifying information. Electronic files for data analysis will contain only the participant code. Codes will not contain any part of the 18 HIPAA identifiers (e.g., initials, DOB, MRN). The key associating the codes and the participants' personally identifying information will be restricted to the Investigator and study staff. The key will be kept secure on a restricted OHSU network drive in a limited access folder.

The study participant's contact information will be securely stored at each clinical site for internal use during the study. At the end of the study, all records will continue to be kept in a secure location for as long a period as dictated by local IRB and institutional regulations. Study participant research data, which is for purposes of statistical analysis and scientific reporting, will be transmitted to and stored within the Knight Cancer Institute per [OHSU's Information Security Directives](#). Individual participants and their research data will be identified by a unique study identification number. The study data entry and study management systems used by clinical sites and by Knight Cancer Institute research staff will be secured and password protected per [OHSU's Information Security Directives](#). At the end of the study, all study databases will be de-identified and archived within the Knight Cancer Institute.

